Study Title: Persistence of Glaucoma Patients With Web-Browser-Based Visual Field Test

Principal Investigator: [name]

NCT Number: NCT05690152

Unique Protocol ID: 202207403

IRB ID: 202207403

Date: 9/5/2025

Web Browser Visual Field Study

PI: [name]
IRB ID #: 202207403

Project Details

I. Project Introduction

I.1

Project to be reviewed by:
IRB-01

I.2

Project Title:
Visual Field Telemedicine in Glaucoma Patients using a Web Browser-Based Test Strategy

I.3

Short Title (optional):
Web Browser Visual Field Study

I.4

Provide a short summary of the purpose and procedures of the study proposed in this IRB application.

- DO NOT include information on studies not proposed in this application.***
- Use LAY terminology only. This must be easily understandable by IRB community members and nonscientists.***
- DO NOT cut and paste technical abstracts from funding applications that may not be understood by a general audience.***

The purpose of this prospective study is to determine the reliability of and patient compliance with a testing strategy with a novel home, web-based visual field test, EyeSimplify (M&S Technologies, Niles, IL), for purposes of surveilling glaucomatous progression. In this study, EyeSimplify will be compared to the current accepted gold standard Standard Automated Perimeter, the Humphrey Visual Field Analyzer (Carl Zeiss Meditec Inc., Dublin, CA).

The proposed study will be conducted at the University of Iowa Hospitals and Clinics and via telemedicine encounters. We estimate 50 subjects will be recruited to participate in the study. Data collected will not include patient identifiers.

Research involves retrospective collection of data, documents, and records, as well as prospective collection of visual field testing performance. The source of data will be retrospective review of computerized or written medical record and testing conducted in clinic beginning upon IRB approval. Patients with suspected, mild, moderate, or severe glaucoma will be included. Clinical data including age, gender, ethnicity, visual acuity, intraocular pressure, severity of disease, Humphry Visual Field performance, EyeSimplify Visual Field performance, and satisfaction survey will be recorded.

Following study recruitment, subjects will be asked to take EyeSimplify visual field tests at home biweekly for six months. They will have no additional responsibilities between tests. Subjects will access the EyeSimplify web browser on their personal electronic devices using a link and login credentials provided to them by a research assistant. Upon logging into the EyeSimplify web browser, subjects will click the "Start Test" button found along the left side of the window and follow the prompts presented on screen to calibrate their screen. Screen calibration involves holding a driver's license/credit card/ID to the screen to ensure the test window is the appropriate dimensions. Following screen calibration, subjects will follow the test prompts presented on screen to complete their visual field test. Test results are automatically sent to the research assistant who issued the exam, so subjects may exit the browser after each test. Upon study completion, subjects will be asked to fill out a brief satisfaction survey.

M&S Technologies is the developer of the EyeSimplify web-based visual field test. [name], [name], and [name] have no financial or intellectual relationship with M&S Technologies, aside from the current study and an additional study under IRB review investigating the Pico Virtual Reality Headset visual field test.

As the developers of the web-based visual field test, M&S Technologies maintains a secure, encrypted, HIPAA-compliant database of EyeSimplify users. This database includes patient profiles containing unique patient IDs (de-identified), birth year, and visual field testing results. Outside of this testing information, M&S Technologies does not have access to any additional patient information.

I.5

Specify your research question(s), study aims or hypotheses (do not indicate "see protocol")
Aim 1: Determine test reliability of the EyeSimplify (M&S Technologies, Niles, IL) home, web-based visual field test in glaucoma patients.
Aim 2: Determine the concordance of EyeSimplify to the Humphrey Visual Field Analyzer (Carl Zeiss Meditec Inc., Dublin, CA) in identifying visual field loss progression.
Aim 3: Determine patient compliance with and tolerance of biweekly EyeSimplify testing for a 6 month period, assessed by test recordkeeping and a patient experience survey.

Primary Hypothesis: The EyeSimplify visual field test will produce reliable visual field testing data.
Secondary Hypothesis: The EyeSimplify visual field test will be non-inferior to the Humphrey Visual Field Analyzer in identifying glaucomatous progression trends.

I.6

Background and significance and/or Preliminary studies related to this project. (do not indicate "see protocol")
Glaucoma is the leading cause of irreversible blindness worldwide (1-2). Standard Automated Perimetry is the current accepted standard for diagnosis and monitoring of glaucomatous visual field loss (3), and the Humphrey Visual Field Analyzer (HFA; Carl Zeiss Meditec Inc., Dublin, CA) is the automated perimeter that is most frequently used due to it currently having the largest market share. The HFA is a useful clinical tool; however, it is a large, expensive device. Testing takes approximately seven minutes per eye when using the Swedish Interactive Threshold Algorithm (SITA) Standard testing algorithm, and testing is typically only done at 6-12 month intervals. Recently, there has been interest in the development of alternative methods to monitor visual field progression outside of the clinic setting (4). EyeSimplify (M&S Technologies, Niles, IL) is a web-based visual field test that aims to increase the frequency at which patients can test their visual fields, improve accessibility to visual field testing, and potentially identify visual field loss progression more quickly.

I.7

Literature cited / references (if attaching a grant or protocol enter N/A).
1. Quigley HA. Number of people with glaucoma worldwide. Br J Ophthalmol. May 1996;80(5):389-93. doi:10.1136/bjo.80.5.389

doi:10.1136/bjo.2005.081224

II. Research Team

II.1

Principal Investigator

Name	E-mail	College
[name]	[contact]	Carver College of Medicine

II.2

Team Members

UI Team Members

Name	E-mail	College	Contact	Key Prsn	UI COI	VAMC COI	Consent Process Involvement	Deactivated
[name]	[contact]	Carver College of Medicine	Yes	Yes	No		Yes	No

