There are no prior research studies investigating the EyeSimplify visual field test.
- VII.B.33** *Have there been any prior IRB reviews (at UI or elsewhere) and/or determinations made with regard to this device?*
No
- VII.B.35** *Has the FDA made an assessment of risk with regard to this device?*
No
- VII.B.36** *Has this device/software been approved by the FDA for another indication or in another form from its use in this project?*
No

VII.C. Project Description (C)

- VII.C.1** *Does this project involve any [research on genes or genetic testing/research](#)?*
No

VII.D. Project Description (D)

- VII.D.1** *Check all materials/methods that will be used in recruiting subjects (you will need to attach copies of all materials at the end of the application):*
- Other - Patients at the University of Iowa Hospitals and Clinics' Glaucoma clinic will be approached at the time of their scheduled appointments to determine if they are interested in participating in this research study.

- VII.D.1.a** *Will any of the materials/methods below be used by researchers (or their colleagues) to recruit subjects into this study?*

- *the potential subject is a patient OR*
- *use of any information considered to be Protected Health Information (PHI) OR*
- *review of patient/clinic records be used in recruiting subjects*

Yes

- VII.D.1.b** *Describe source of records*

Patients at the University of Iowa Hospitals and Clinics' Glaucoma clinic will be approached at the time of their regularly scheduled appointments to participate in this research study.

- VII.D.1.c** *Select all Private Identifiable Information (PII) or Protected Health Information (PHI) accessed and used for this study (select all that apply)*

Identify types of PHI accessed

Type of PHI	Data source
Name	
Street address	
City	
County	
Precinct	
Zip code	
Geocodes smaller than state	
Date of birth, ages > 89 years of age	
Diagnosis dates	
Procedure dates	
Admission or discharge dates	
Telephone numbers	
Fax numbers	
E-mail addresses	
Social Security number	

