- Describe study populations separately if they will be participating in different procedures - include CONTROL population if applicable.*
- DESCRIBE:**
- *What subjects will be asked to do/what happens in the study (in sequential order)*
 - *The time period over which procedures will occur*
 - *The time commitment for the subject for individual visits/procedures*
 - *Long-term followup and how it occurs*
- Potential subjects will be approached at the time of their regularly scheduled appointment to participate in this research study. The research assistant will answer any questions potential subjects may have regarding the purpose, procedure, and risks of the study. If they agree to participate, subjects will sign an informed consent.
- In addition to routinely scheduled clinical examination, including visual field testing (VF) with the Humphrey Field Analyzer (HFA), subjects will be asked to complete biweekly VF for six months using EyeSimplify, a novel, web-based VF, at home. Subjects will be instructed to complete the EyeSimplify VF in a quiet, dark room free of distractions. The research assistant will be available via email or telephone to troubleshoot any issues that may arise.
- The EyeSimplify uses a 24-2 examination protocol with a Neighborhood-Zippy Estimation by Sequential Testing (ZEST) testing algorithm. Background brightness will be set to 15.8 ASB. The test will use a scaled white stimulus. Subjects will self-administer the EyeSimplify VF at home. The EyeSimplify VF will be deemed unreliable if FP >15%. The HFA uses a 24-2 examination protocol with a SITA standard testing algorithm. A clinical technician will administer the HFA VF at the University of Iowa Hospitals and Clinics' Glaucoma clinic. The HFA VF will be deemed unreliable if FP >15%. At the conclusion of the study, subjects will complete a satisfaction survey regarding testing using the EyeSimplify VF.
- VII.E.7** *Will you attempt to recontact subjects who are lost to follow-up?*
Yes
- VII.E.8** *Describe - any procedures need to be included in the consent:*

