- Electronic records (computer files, electronic databases, etc.) - All electronic files will be kept as files on an encrypted, password-protected UIHC Department of Ophthalmology network server. There will be no identifiers or link available on any transferred data; therefore, there will be no way to compromise patients' privacy or confidentiality.
 - Name - [name]
 - Title - Senior IT Support Consultant
 - University Job Classification - Faculty/Staff
- Paper/hard copy records (hard copy surveys, questionnaires, case report forms, pictures, etc.) - Informed consent documents will be transported directly from the UIHC Glaucoma clinic to a locked file cabinet in the PI's office within the Department of Ophthalmology and Visual Sciences immediately following the study recruitment clinical encounter by the PI or research assistant. These documents will remain in this locked cabinet for the duration of the study.

X.5 Do the confidentiality protections indicated above allow only members of the research team to access the data/specimens?

No

X.6 Describe

M&S Technologies, the developers of the EyeSimplify web-based visual field test, maintain a secure, encrypted, HIPAA-compliant database of patient testing information. This database includes study ID (de-identified), birth year, and experimental visual field testing data. M&S Technologies does not have access to any additional patient information.

X.7 Does your study meet the NIH criteria for a [Certificate of Confidentiality](#) or will you be applying for Certificate of Confidentiality?

No

XI. Data Analysis

XI.1 Describe the analysis methods you will use, including, if applicable, the variables you will analyze

Variables: Clinical data including age, gender, ethnicity, Humphry Visual Field performance, EyeSimplify Visual Field performance, and satisfaction survey will be collected and analyzed.

Data analysis: Humphrey Visual Field Guided Progression Analysis (GPA) and EyeSimplify Visual Field mean deviation linear trending will be compared using Bland-Altman analysis.

XI.2 Provide the rationale or power analysis to support the number of subjects proposed to complete this study.

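### The home MD slope is sensitive to practice and display drift, and the plan has no device rule, device record or sensitivity analysis to expose it

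*Combined protocol and SAP*

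**What the plan says.** Section XI.1 gives the whole analysis of progression: HFA Guided Progression Analysis and "EyeSimplify Visual Field mean deviation linear trending will be compared using Bland-Altman analysis". It names no other model term and does not say that any home test is left out of the trend.

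The data behind the trend are described in I.4 and VII.E.6. On schedule, "subjects will be asked to take EyeSimplify visual field tests at home biweekly for six months". On equipment, "Subjects will access the EyeSimplify web browser on their personal electronic devices". The only calibration described is in I.4: "Screen calibration involves holding a driver's license/credit card/ID to the screen to ensure the test window is the appropriate dimensions". VII.E.6 adds a scaled white stimulus, the statement that "Background brightness will be set to 15.8 ASB", and an instruction to test in a dark, quiet room. The home test is self-administered; a technician runs the HFA in clinic. The only validity rule for a home test is a false-positive rate of at most 15%.

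On prior experience, VII.B.32 says: "There are no prior research studies investigating the EyeSimplify visual field test". VII.D.28 starts testing within a week of consent, and no training test is mentioned. Device does not appear among the variables in I.4 or XI.1. The platform log described in VII.B.21 covers when a test is completed, not what it was taken on.

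**The concern.** A straight line through MD against time attributes every sustained change to the passage of time. Two other sources of change are plausible here. Subjects may improve over the first few tests as they learn an unsupervised task, and the display may change when they switch device or alter its brightness. Nothing in the plan prevents, records or adjusts for either.

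Six months is short, so a small artefact becomes a large annual rate. A true loss of 1 dB/year is only 0.5 dB over the study. Early practice pushes the slope upward and can hide loss. A lasting downward step imitates progression, and an upward one hides it. These sources belong to the home test, because the HFA is run by a technician in clinic. They therefore carry into the comparison on which Aim 2 and the secondary hypothesis depend.

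**Working it through.** The plan gives no figure for slope precision or drift, so there is none to reproduce. What can be calculated is how strongly the slope responds to a given artefact.

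**Inputs.**
- Schedule: biweekly for six months (I.4). The word is not defined. I take 13 tests two weeks apart (24 weeks from first to last), with 52 tests over half a year as the alternative.
- Artefact sizes, learning speed and test-retest SD: the documents give none. All are assumptions.

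**Formula.** For an artefact d(t) added to MD, the least-squares slope shifts by Σ(t − t̄)d(t)/Sxx, with Sxx = Σ(t − t̄)².

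**Leverage with 13 tests.** Sxx = 182 × (2/52)² = 0.2692 year². The first test is 12/52 = 0.2308 year from the mean, so its weight is −0.2308/0.2692 = −0.857 per dB; the second is −0.714.
- First test 1 dB too low: +0.86 dB/year.
- First test 1 dB and second 0.5 dB too low: 0.857 + 0.357 = +1.21 dB/year.
- The last test has the same leverage as the first, with the opposite sign.

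**Lasting step of 1 dB.** The shift is the sum of the weights after the step.
- Step after test 1, or affecting only test 13: 0.86 dB/year.
- Step before test 4: 2.14 dB/year.
- Step at mid-study: (1+2+3+4+5+6) × (2/52)/0.2692 = 3.0 dB/year, the maximum. A 0.5 dB step there gives 1.5.

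**With 52 tests.** Sxx = 1.126. A first test 1 dB too low shifts the slope by 0.25/1.126 = 0.22 dB/year. A 1 dB mid-study step still shifts it by 2.9.

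**Gradual practice.** Let the gain after k earlier tests be A(1 − exp(−k/τ)), with A = 1 dB.

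| τ (tests) | Bias, 13 tests | Bias, first two dropped | Bias, 52 tests |
|---|---|---|---|
| 1 | +1.22 | +0.22 | +0.34 |
| 2 | +1.62 | +0.77 | +0.53 |
| 4 | +1.87 | +1.35 | +0.87 |

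All biases are in dB/year and scale in proportion to A.

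**Against random error.** At an assumed test-retest SD of 1 dB, one subject's slope has SE 1/√0.2692 = 1.93 dB/year. Dropping one test gives 2.17 (13% larger) and dropping two gives 2.48 (29% larger). XI.2 cites a precedent in which 20 of 47 were analysed; applied to 50 subjects, that is about 21. Measurement error in a mean slope over 21 subjects is then 1.93/√21 = 0.42 dB/year (this ignores true differences between subjects). A practice bias shared by all subjects does not shrink with averaging.

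**Effect on the Bland-Altman result.** Drift common to all subjects moves the mean difference. Drift that varies between subjects widens the limits of agreement. Brightness that varies haphazardly from test to test adds noise to each slope but no systematic drift.

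**The case against.** Four stronger readings are tempting, and the documents do not support them.

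*Screen luminance is uncontrolled.* The calibration sentence comes from a lay summary, where technical detail would be left out. VII.E.6 states a background value, a scaled stimulus and a dark room. The platform may do more than is described. What stands is narrower: no means of reaching or verifying that value on a personal screen is described.

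*Subjects are first-time users, so a practice effect is present.* VII.B.32 reports no earlier studies, which is not the same as no earlier use. First-time use is a fair inference for a novel test, but the plan neither states it nor records prior use.

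*The slope is wrong by 1 to 3 dB/year.* Every dB artefact above is assumed, the mid-study step is the worst position, and 52 tests would cut the practice effect considerably.

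*The first test should be excluded from the main analysis.* That is a trade-off. With the first test 1 dB low and SD 1 dB, the root mean squared error of one subject's slope is √(0.857² + 1.927²) = 2.11 dB/year with all 13 tests, against 2.17 after dropping it. At SD 2 dB the figures are 3.95 and 4.35. Dropping it helps a single slope only at lower noise (SD 0.5 dB: 1.29 to 1.09), or where the aim is to remove a shared group bias. The first home test may also be the one closest in time to a clinic HFA, since recruitment is at a clinic appointment and testing starts within a week.

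It can also be argued that learning and display variation are part of how a home test performs in real use, so removing them would flatter the product. That is a good reason to keep those tests in the main result. It is not a reason to leave the source of a disagreement unidentifiable.

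**Conclusion.** The concern holds in a limited form. As written, the plan cannot separate disease from learning or display change in the home MD slope, and collects nothing that would let a reader try. The sensitivity follows exactly from the schedule. Assuming 13 tests, each dB of error in the first test moves the slope by 0.86 dB/year, and each dB of lasting step by 0.86 to 3.0. With 52 tests, the first-test figure falls to 0.22 and the mid-study step stays near 2.9.

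How much drift would occur cannot be taken from the documents, so this is a demonstrated exposure, not a demonstrated bias. A shared drift would show in the Bland-Altman mean, but the plan would have no way to tell learning or hardware from a real difference between the tests. It is worth acting on because the remedy is nearly free. It bears mainly on the secondary, progression question. Exclusion of tests from the main analysis is not warranted.

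**What to change.** 1. Add to the test instructions in VII.E.6 that subjects use one device, at one fixed brightness setting with auto-brightness off, for all tests. Record the device used at each test. A device type or simple label is enough; no serial number is needed.

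2. State in XI.1 that all home tests meeting the false-positive rule enter the main slope and agreement analyses. Pre-specify three sensitivity analyses: without the first test, without the first two, and without tests taken after a device change.

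The cost is one instruction line, one data field and one analysis sentence. On 13 tests, the sensitivity slopes have SEs 13% larger (one test dropped) or 29% larger (two dropped). The early-test analyses are a diagnostic, not a cure: if learning is slow, a 1 dB practice gain still leaves +0.77 to +1.35 dB/year after two tests are dropped.

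The document includes an IRB closure notice, so the device instruction and record can only serve a later protocol. The early-test analyses need only the stored test series and could accompany a report of this study, labelled as not pre-specified.

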 - ☐ **Phase III trials** – include expanded controlled and uncontrolled trials after preliminary evidence suggesting effectiveness of the drug has been obtained, and are intended to gather additional information to evaluate the overall benefit-risk relationship of the drug and provide an adequate basis for physician labeling ([ClinicalTrials.gov](https://clinicaltrials.gov) & [FDA](https://www.fda.gov))
 - ☐ **Phase IV trials** – studies of FDA-approved drugs to delineate additional information including the drug’s risks, benefits, and optimal use ([ClinicalTrials.gov](https://clinicaltrials.gov) & [FDA](https://www.fda.gov))
- VII.B.11 *Is there a separate, written protocol that will be submitted in addition to this IRB New Project form? (Note: a grant application is not considered to be a protocol)*

- VII.B.2** *Does this project involve a [drug washout](#) (asking subject to stop taking any drugs s/he is currently taking)?*
No
- VII.B.6** *Will any subjects receive a [placebo](#) in this study when, if they were not participating, they could be receiving an FDA-approved treatment for their condition?*
No
- VII.B.18** *Does this project involve the evaluation, or testing, of the safety and/or efficacy of a medical device?*
Yes
- VII.B.19** *Describe in detail procedures in place for maintaining device shipment and receipt records:*
EyeSimplify is a web browser-based visual field test and, therefore, will not require shipment or receipt records.
- VII.B.20** *Who will be responsible for maintaining these shipment and receipt records?*
EyeSimplify is a web browser-based visual field test and, therefore, will not require shipment or receipt records.
- VII.B.21** *Describe in detail procedures in place for tracking use and disposition of devices described in this study:*
The EyeSimplify web browser automatically tracks when subjects complete a visual field test and no additional physical record will be kept to minimize risk of loss of confidentiality.
- VII.B.22** *Who will be responsible for maintaining these use and disposition tracking records?*
The EyeSimplify web browser automatically tracks when subjects complete a visual field test and no additional physical record will be kept to minimize risk of loss of confidentiality. The PI and key research personnel will have access to the EyeSimplify web platform; however, M&S Technologies maintains this secure, encrypted, HIPAA-compliant database.

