If a subject fails to complete a scheduled home visual field test, the PI or research assistant will reach out to the patient via email and/or telephone to determine the cause of the missed test. If the patient can be contacted and wishes to continue participating in the study, the PI or research assistant will prompt the subject to complete the exam. If a patient misses a second scheduled test, the patient will be considered lost to follow-up and will not be contacted again.
- VII.E.9** *Will subjects be provided any compensation for participating in this study?*
No

VIII. Risks

- VIII.1** *What are the risks to subjects including*
- *emotional or psychological*
- *financial*
- *legal or social*
- *physical?*
Loss of time and confidentiality
- VIII.2** *What have you done to minimize the risks?*
- *If applicable to this study ALSO include:*
 - *How you (members of your research team at Iowa) will monitor the safety of individual subjects.*
 - *Include a description of the availability of medical or psychological resources that subjects might require as a consequence of participating in this research and how referral will occur if necessary (e.g. availability of emergency medical care, psychological counseling, etc.)*

Patient privacy will be protected by separating patient identifiers from the data and storing the data on a password-protected computer in a locked office within the Ophthalmology Department. To prevent a loss of confidentiality from occurring, all data will be located on a UIHC encrypted, password-protected Department of Ophthalmology server. Only designated research team members and PI will have access to the drive. Any paper documents will be kept in a locked file cabinet in the principal investigator's office.

All data collected by M&S Technologies will be stored in a secure, encrypted, HIPAA-compliant database. De-identified subject data is ultimately aggregated for quality improvement purposes by M&S Technologies.

The study utilizes data generated as a consequence of routine clinical practice, as well as additional home, web-based visual field tests. The study poses no therapeutic questions and no interventions; no treatment is directed by the study. Therefore, the study poses no substantive risk to the patient other than loss of time and confidentiality. It does not impose any significant burden on the patient.

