A similar study investigating home visual field testing using the Melbourne Rapid Fields iPad application (Glance Optical Pty., Ltd., Melbourne, Australia) recruited 47 subject, of which 43% (n = 20) were analyzed (Prea SM, Vingrys AJ, Kong GYX. Test Reliability and Compliance to a Twelve-Month Visual Field Telemedicine Study in Glaucoma Patients. J Clin Med. Jul 25 2022;11(15)doi:10.3390/jcm11154317).

XII. Future Research

XII.1 Do you wish to keep any information about subjects involved with this research project so that members of the current research team may contact them in the future for your own research projects?

No

XII.2 *Do you wish to keep any information about subjects involved with this research project so that [other researchers](#) may contact them for future research?*
No

XII.4 *Does this project involve storing any data, tissues or specimens for future research?*
Yes – contribution(s) for future use is mandatory for participation in the study

**Human Subjects Office/
Institutional Review Board (IRB)**

[name]
[name]
[name]
[contact] [contact]
[contact]
<http://research.uiowa.edu/hso>

IRB ID #: 202207403

To: [name]

From: IRB-01 DHHS Registration # IRB000000099,
Univ of Iowa, DHHS Federalwide Assurance # FWA00003007

Re: Visual Field Telemedicine in Glaucoma Patients using a Web Browser-Based Test Strategy

Protocol Number:

Closure Date: 09/05/25

Source of Support: American Glaucoma Society

Investigational New Drug/Biologic Name:
Investigational New Drug/Biologic Number:
Name of Sponsor who holds IND:

Investigational Device Name:
Investigational Device Number:
Sponsor who holds IDE:

The following documents have been submitted with the closure notification:
No new attachments.

This closure is acknowledged and has been electronically filed. IRB approval is no longer valid for the above-named project.

Study Closure: Closing a study with the IRB is a permanent action and cannot be undone. The PI is required to notify all research team members and participating research sites (as applicable) of the closure. Closing a project means:

- The research is permanently closed to accrual/enrollment
- All subjects have completed all research related activities
- Collection and use of private identifiable information is complete
- Analysis of private identifiable information is complete

The following applies to this research even after study closure:

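### The satisfaction survey reaches only subjects who persisted, so the self-reported part of Aim 3 is selected and probably, though not certainly, biased upward

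*Combined protocol and SAP*

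**What the plan says.** Aim 3 (I.5) is to "Determine patient compliance with and tolerance of biweekly EyeSimplify testing for a 6 month period, assessed by test recordkeeping and a patient experience survey". It therefore has two instruments, the test log and the survey.

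Two places give the timing of the survey. I.4 has: "Upon study completion, subjects will be asked to fill out a brief satisfaction survey". The procedures in VII.E.6 agree: "At the conclusion of the study, subjects will complete a satisfaction survey regarding testing using the EyeSimplify VF". Neither describes an interim, exit or withdrawal survey.

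VII.E.8 deals with missed tests. After the first, the team "will reach out to the patient via email and/or telephone to determine the cause of the missed test". After the second, the rule is: "If a patient misses a second scheduled test, the patient will be considered lost to follow-up and will not be contacted again".

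The test log is automatic (VII.B.21): "The EyeSimplify web browser automatically tracks when subjects complete a visual field test".

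The analysis section (XI.1) lists the survey among the variables but names only a Bland-Altman comparison of the two perimeters. It gives no denominator for the survey, no handling of survey non-response, and no variable for the reason a test was missed.

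**The concern.** Each rule is reasonable alone, but together they make answering the survey conditional on persistence. A subject with two missed tests cannot be asked, and nothing says that a subject who actively withdraws will be asked. People who could not calibrate the screen, disliked the test or found the schedule too heavy are plausibly over-represented among those who stop, and the survey does not reach them.

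At stake is how the satisfaction result can be read. Section IX.2 looks to less discomfort and wider access as benefits of home testing. A figure from persisters describes people for whom home testing worked well enough to continue. It does not describe the clinic population that would be offered it.

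**Working it through.** **The plan's own figure.** XI.2 cites a study that "recruited 47 subject, of which 43% (n = 20) were analyzed". Check: 20/47 = 0.426, which rounds to 43%. Applied to 50 subjects, 50 × 20/47 = 21.3, so about 21 would be surveyed and about 29 would not. This is the only retention-like figure in the documents. It is used below as one end of a range.

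**Inputs**
- Retention r: 0.43 (from XI.2, illustrative) and 0.80 (assumed, milder case).
- Share of completers satisfied, s: 0.80 (assumed).
- Share of non-completers satisfied, d: 0.40 to 0.60 (assumed).

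**Formulas**
- Satisfaction among all enrolled: r·s + (1 − r)·d.
- Overstatement by the completer figure: s minus the above, which equals (1 − r)(s − d).
- Bounds with nothing known about non-completers: from r·s (none satisfied) to r·s + (1 − r) (all satisfied).

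**At r = 0.43**
- d = 0.40: 0.344 + 0.57 × 0.40 = 0.572, an overstatement of 0.228.
- d = 0.60: 0.344 + 0.57 × 0.60 = 0.686, an overstatement of 0.114.
- Bounds: 0.344 to 0.344 + 0.57 = 0.914.

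**At r = 0.80**
- d = 0.40: 0.64 + 0.20 × 0.40 = 0.72, an overstatement of 0.08.
- d = 0.60: 0.64 + 0.20 × 0.60 = 0.76, an overstatement of 0.04.
- Bounds: 0.64 to 0.64 + 0.20 = 0.84.

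| Retention | True figure when 80% is reported | Overstatement | Bounds |
|---|---|---|---|
| 43% | 57–69% | 11–23 points | 34–91% |
| 80% | 72–76% | 4–8 points | 64–84% |

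**How strict the two-miss rule is, without the cited study.** Assume that biweekly means every two weeks (about 13 tests), that misses are independent with probability q per test, and that any two misses count, consecutive or not. The chance of at most one miss is (1 − q)^13 + 13q(1 − q)^12.
- q = 5%: 86%, about 43 of 50.
- q = 10%: 62%, about 31 of 50.
- q = 15%: 40%, about 20 of 50.

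In practice misses cluster within people, so these values only show that modest miss rates can remove many subjects from the survey.

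**The case against.** The strongest reply has five parts.

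- **Test records cover everyone.** This stands. The log is automatic, so compliance and persistence, the subject of the study title, are measured in all enrolled subjects. Stopping is also behavioural evidence about tolerance. A reader might infer that tolerance as a whole is measured only in people who tolerated the test. The documents do not support that: only the self-reported part is selected, and persisting is not the same as tolerating. A dissatisfied subject can finish, and a satisfied one can miss two tests for unrelated reasons.
- **The reason is already sought.** This stands in part. Every two-miss subject is due a contact attempt about the cause of the first miss. But that reason is not listed in XI.1, it concerns the first miss rather than the final stop, and none is sought after the second.
- **The result could be adjusted.** A reader might infer that no analysis can help. That goes too far. I.4 provides for age and disease severity, and the log holds tests taken before stopping, so weighting is possible and bounds always are. Weighting, however, must assume that persisters and non-persisters with the same recorded characteristics are equally satisfied, which cannot be tested without survey data from those who stopped. No such analysis is planned.
- **The 43% is borrowed.** This stands. It is a share analysed, not a share retained, from another product over twelve months rather than six. The plan never adopts it as a dropout rate, and for that reason retention is varied above.
- **No hypothesis concerns satisfaction.** This is true and limits the weight of the point. The primary hypothesis is reliability, and the survey serves the third aim.

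**Conclusion.** The concern holds for self-reported satisfaction. Following I.4, VII.E.6 and VII.E.8 as written, the survey result comes only from subjects with at most one missed test. Reading study completion as the end of the whole study, rather than of each subject's six months, does not help: the no-contact rule still bars the survey for two-miss subjects.

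The selection follows from the text. Upward bias is likely, not certain; the direction would reverse if those who stopped were the more satisfied group. With the assumed satisfaction rates, the overstatement runs from 4–8 points at 80% retention to 11–23 points at 43%. The bounds need no assumption about non-completers, but they do depend on retention and on the 80% taken for completers. The survey itself is an attachment not in the file, so whether it yields a single satisfied share is also assumed.

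This is worth correcting because a named aim is affected and the change is cheap. It does not touch the compliance result or the primary hypothesis.

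**What to change.** **If subjects can still be contacted, or the design is reused**
- Amend I.4, VII.E.6 and VII.E.8 together so that they agree. Offer the existing survey once to every enrolled subject at the earlier of stopping or six months.
- Exempt this single contact from the no-contact rule, except after withdrawal of consent. Update the consent document if needed, since the VII.E.8 prompt ties recontact procedures to consent.
- Record the reason for missing or stopping, including the answer given after the first miss, and add it to the variables in XI.1.
- In XI.1, state that the survey response rate will be given out of all enrolled, that results will be shown separately for completers and non-completers, and that best- and worst-case bounds will cover non-response.

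**If data collection is over.** The IRB closure notice, dated 09/05/25, suggests that it is. Label the satisfaction result as completers-only, give the number surveyed over the number enrolled, and show the bounds.

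**Cost.** A few sentences of text, one extra contact per stopped subject and possibly a minor consent change. Some stopped subjects will not answer, so the bounds will narrow rather than close.
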